4.3 Randomization and Blinding

Only Patients who meet all the inclusion criteria shall be randomly enrolled in this study. In the event that an ineligible patient is randomized, or erroneously start the treatment, or an enrolled subject no longer meets the eligibility criteria before starting the study treatment, the sponsor's representative and the investigator must jointly discuss whether the subject should continue or withdraw from the study. The sponsor should ensure that appropriate documentation is retained with regards to such decisions.

This study is an open-label study and does not involve blinding.

4.4 Rescreening Criteria

In this study, rescreening is allowed. That is, subjects who sign the informed consent form and enter the screening process but do not meet the inclusion criteria and have not yet started the treatment may be rescreened. Test/examination results from the first screening that meet the inclusion/exclusion criteria may be reused in the rescreening, provided that they are within the window period. During rescreening, a new subject No. is assigned.

4.5 Withdrawal or Discontinuation

Subjects may withdraw the informed consent and withdraw from the study at any time. The investigator can determine whether the subject needs to withdraw from the study based on the occurrence of AEs. In addition, if the subject is not eligible for enrollment or violates the protocol, or due to management and/or other safety reasons, the investigator or the sponsor may withdraw the subject from the study.

4.5.1 Study withdrawal criteria

Reasons for withdrawal may include:

- Withdrawal of informed consent and refusal of further follow-ups by subjects;
- Continuing participation in the study violating the patient's optimal benefit due to clinical AEs, laboratory abnormalities, or concurrent diseases, as assessed by the investigator;
- Other investigator-assessed reasons, such as the inability to provide voluntary consent due to imprisonment or quarantine, or significant protocol violations;
- Lost to follow-up;
- Death;
- Study termination by the sponsor.

The reasons for the subject's withdrawal from the study must be recorded in CRF and the subject's medical record.

It is noteworthy that withdrawal of informed consent refers to the subject withdrawing the consent to be further contacted, or no longer agreeing to provide information via a previously authorized person. Whenever possible, subjects should notify the investigator in writing that they no longer agree to be followed. The investigator should specify and record the withdrawal of the informed consent. That is, whether the subject no longer consents to continue study treatment, or whether the subject no longer consents to receive the follow-up visits specified in the protocol either.

4.5.2 Criteria for treatment discontinuation

The study treatment must be discontinued when any of the following occurs:

- Requests to discontinue the study treatment by subjects;
- Radiographic or clinical evidence of progressive disease, unless the subject meets the criteria for continuing treatment beyond progression (see Section 4.6);
- Occurrence of pregnancy during the study;
- Any clinical AEs, laboratory test abnormalities, or other medical conditions indicating that the subject can no longer benefit from the treatment;
- Comprehensive deterioration of health status and inability to continue study participation;
- Significant protocol deviations such as ineligibility found after enrollment or incompliance;

- Lost to follow-up;
- Study termination by the sponsor;
- Death;
- Other reasons as determined by the investigator.

4.5.3 Procedures for withdrawal or discontinuation

The efficacy and safety examinations to be completed upon study withdrawal as specified in the protocol must be completed as much as possible. In addition, the safety follow-up should be completed along with fully documented AEs and their outcomes. The investigator can recommend or provide new or alternative treatments to a subject based on the condition of the subject. Subjects showing no progressive disease should continue to be followed up for imaging evaluation as much as possible, until the start of a new anti-tumor treatment or progressive disease.

Unlike subjects withdrawing their informed consent to withdraw from the study, subjects who request discontinuation of study treatment will remain in the studies and should be followed up according to the study procedures specified in the protocol.

Survival status should still be followed even if the subject refuses further visits, unless the subject withdraws the consent to provide further information or the consent to be further contacted. In such case, no study assessment is performed, nor any data are collected.

4.6 Criteria for Continuing Treatment Beyond Disease Progression

Some subjects receiving immunotherapy can still benefit from continuing treatment after radiographic progression. The tumor of some subjects may be enlarged, but remarkable necrosis or denaturation may occur inside the tumor, with CT showing decreased internal density of the tumor lesion. It is generally considered to be beneficial to subjects under this circumstance. The study treatment may be continued beyond progressive disease (PD) defined per RECIST 1.1 for subjects who meet the criteria below:

- The investigator deems that it is in the best interest of the subject to continue treatment, and subject is not required to start other anti-tumor treatment immediately;
- The subject is able to tolerate continued study treatment;
- No obvious deterioration in subject's performance status, and no marked worsening of cancer-related symptoms;
- Subjects must sign the informed consent form prior to continuing study treatment, in which potential risks, discomforts, and other treatment options shall be included;
- Continued study treatment must be reviewed and approved by the principal investigator of the study center.

The assessment of clinical benefit must consider whether the subject has clinical exacerbations and whether the subject can benefit from continuing treatment. It is recommended that the investigator should discuss with the sponsor whether the subject should continue treatment after the disease progression.

If it is decided that the subject will continue the study treatment beyond progression, the subject should continue to be treated, evaluated, and followed up according to the protocol requirements.

Subjects should withdraw from the study if further disease progression is observed at the next assessment. The initial date of investigator-assessed progression should be used for all statistical analyses involving progression, regardless of whether the subject continues the study treatment beyond progression.

If the subject discontinues treatment due to deterioration of the general condition without objective evidence for progressive disease, the progression will be reported as "general deterioration". More objective evidences (eg., imaging confirmation) of progressive disease of these subjects should be obtained whenever possible after treatment discontinuation.

For subjects who withdraw from the study due to unacceptable toxicity without radiographic disease progression observed, the imaging examination should be performed at the same frequency, until PD or initiation of other anti-tumor treatments. The radiographic evidence of PD of these subjects must be obtained whenever possible.

4.7 Termination or Suspension of Study

This study can be terminated early or suspended if there are sufficient reasons. This may result from the decision of the regulatory authorities, changes in comments by the ethics committee, efficacy or safety issues of the study medications, or the judgment of the sponsor. In addition, the sponsor reserves the right to terminate the research and development of SHR-1210 at any time.

The party who decides to suspend/terminate the study should notify the investigator, sponsor, and regulatory authorities in writing, documenting the reasons for suspension/termination. The investigator must immediately notify the ethics committee and sponsor, and provide relevant reasons.

The reasons for termination or suspension of the study may include:

- Confirmed unexpected, major, or unacceptable risks to the subjects;
- Existing efficacy data supporting study termination;
- Confirmed ineffectiveness of the study treatment;
- A major error in the protocol found during the implementation of the study;

- Extreme difficulties in completing the study due to poor compliance with protocol, such as severe delays in subject recruitment or frequent protocol deviations;
- Incomplete or undetectable data;
- Changes in the sponsor's development strategy for the investigational drug;
- Valueless study results.

The study may continue once that issues related to drug safety, protocol compliance, and data quality have been resolved and approved by the sponsor, ethics committee, or CFDA (now NMPA).

4.8 Definition of End of Study

End of the study is defined as the last subject last visit (LSLV) or the last subject completing 24 months of study treatment after enrollment (whichever occurs first).

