5.2 Dose Modification of Study Drugs

5.2.1 Dose modification of SHR-1210

Dose increases and reductions of SHR-1210 are not permitted. If SHR-1210 treatment is interrupted due to a toxicity, the subject may resume the treatment at the original dose after the toxicity is resolved. AEs related to SHR-1210 may be immune toxicities, and may occur shortly after the first dose or several months after the last dose. If the conditions listed in [Table 7](#) occur, the use of SHR-1210 should be interrupted. During the study, the investigator must consult with the sponsor if the investigator considers that an adjustment listed in [Table 7](#) is inappropriate based on the benefit-to-risk ratio of subjects or that SHR-1210 treatment should be interrupted or resumed due to a condition not listed in the table.

Table 7. Dose modification criteria for SHR-1210 due to immune-related toxicity

SHR-1210-Related Toxicity	Grade for Interruption	Resumption	Discontinuation
Diarrhea/Colitis	Grade 2-3	Recovered to Grade 0-1	Toxicity has not resolved by 12 weeks after the last dose, or the corticosteroid dose cannot be reduced to prednisone 10 mg/day (or equivalent) or lower within 12 weeks after the last dose.
	Grade 4	Discontinuation	Discontinuation
AST/ALT or Bilirubin Increased	Grade 2	Recovered to Grade 0-1	Toxicity has not resolved by 12 weeks after the last dose, or the corticosteroid dose cannot be reduced to prednisone 10 mg/day (or equivalent) or lower within 12 weeks after the last dose.
	Grade 3-4	Discontinuation ^a	Discontinuation
Type 1 Diabetes Mellitus (new onset) or Hyperglycemia with Signs of β-cell Failure	Grade 3-4 or new-onset type 1 diabetes	SHR-1210 treatment may only be resumed after the clinical and metabolic conditions of the subject are stabilized.	
Hyperthyroidism	Grade 3	Toxicity reduced to Grade 0-1	Toxicity has not resolved by 12 weeks after the last dose, or the corticosteroid dose cannot be reduced to prednisone 10 mg/day (or equivalent) or lower within 12 weeks after the last dose.
	Grade 4	Discontinuation	Discontinuation
Hypothyroidism	Grade 2-4	Study treatment can be continued after starting thyroxine replacement therapy	

SHR-1210-Related Toxicity	Grade for Interruption	Resumption	Discontinuation
Pneumonia	Grade 2	Toxicity reduced to Grade 0-1	Toxicity has not resolved by 12 weeks after the last dose, or the corticosteroid dose cannot be reduced to prednisone 10 mg/day (or equivalent) or lower within 12 weeks after the last dose.

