5.3 Duration of Treatment

All subjects should continue to receive the study treatment until progressive disease, intolerable toxicity, voluntary treatment discontinuation or study withdrawal by the subject, or discontinuation determined by the investigator.

SHR-1210 is an immune checkpoint inhibitor and according to the experience of similar drugs, some subjects may experience delayed or early pseudo progression after receiving immunotherapy drugs. For subjects in the treatment group experiencing progressive disease (PD) for the first time, they may continue with the SHR-1210 treatment if they meet the criteria in section 4.6 Criteria for Continuing Treatment Beyond Disease Progression. Subjects who do not have progressive disease or intolerable toxicities may continue the SHR-1210 treatment for no more than 24 months. Subjects who do not have progressive disease after 24-month treatment may continue the apatinib monotherapy according to the prescribing information of apatinib.

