6.4 Follow-up period

6.4.1 Safety follow-up period

Safety follow-up starts from the last dose of study treatment. The follow-up is performed once every 30 days (\pm 7 days) until 90 days after the last dose.

The first safety follow-up (30 days \pm 7 days) is carried out at the study center where the evaluations specified in the protocol are completed. The second (60 days \pm 7 days) and the third (90 days \pm 7 days) follow-up are made via telephone calls. The information on survival, concomitant medications/concomitant treatments and AEs are collected.

- ◆ During the first safety follow-up (30 ± 7 days), the subjects should receive the following evaluations at the study center (if the subject has started a new anti-tumor treatment before the first safety follow-up, then the follow-up should be completed before starting the new anti-tumor treatment):
 - ECOG PS
 - Vital signs
 - Physical examination: Specific physical examination is performed if clinically indicated.
 - Hematology
 - Urinalysis
 - Fecal occult blood
 - Clinical chemistry
 - Thyroid function

- Coagulation function
 - ECG
 - Collection of AEs
 - Documentation of concomitant medications/concomitant treatments
- ◆ For the second (60 days after the last dose) and the third safety follow-ups (90 days after the last dose), the subjects' survival information and AEs can be collected via telephone calls.
- ◆ Imaging examination: Subjects without radiographically confirmed disease progression should receive imaging examination at the same frequency as that during the treatment period.

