7.4.3 Reporting of serious adverse events

Serious adverse events (SAEs) that occur from the signing of the informed consent form until 90 calendar days (inclusive) after the last dose will be collected. In the event of an SAE, whether it is an initial report or a follow-up report, the investigator must complete the "NMPA Serious Adverse Event Report Form" immediately, with a signature and date. It must have been reported to the relevant regulatory authorities, the sponsor, and the ethics committee within 24 hours of knowing of the event.

The sponsor's email address for safety data is: [contact].

SAEs that occurred 90 days after the last study dose were generally not reported unless they were suspected to be related to the study drugs. The symptoms, severity, causality with the study drug, time of onset, time of treatment, measures taken, time and method of follow-up, and outcome should be documented in detail in the SAE report. If the investigator believes that an SAE is not related to the study drug but potentially related to the study conditions (such as the discontinuation of past treatment, or comorbidities during the study), the causality should be explained in the description section of the SAE report form. If the severity of an ongoing SAE or its relationship to the study drug changes, a follow-up report should be submitted immediately. If an error is found in a previously reported SAE, such SAE may be revised, revoked, or downgraded in follow-up reports and reported in accordance with the SAE reporting procedure.

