14 EXPECTED STUDY SCHEDULE

Anticipated enrollment of the first subject: Dec. 2017

Anticipated enrollment of the last subject: Dec. 2018

Anticipated study completion: Dec. 2020

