### 11.4.1 Adverse event

An adverse event (AE) refers to any untoward medical occurrence in a study subject administered a medicinal product and which does not necessarily have a causal relationship with this treatment. In this study, AE should be collected from the signing of informed consent form (ICF) to 90 days after the last dosing of study drugs. AE includes any adverse symptom or sign, laboratory test abnormality, or disease. AE will be summarized separately in different stages of cohort 1 (SHR-1210 + capecitabine + oxaliplatin, sequence by SHR-1210 + apatinib mesylate, and total) and cohort 2.

AE will be analyzed based on treatment-emergent adverse event (TEAE). TEAE is defined as an AE that occurs or becomes aggravated on the same day or after the first dosing of study drugs but not later than 90 days after the last dosing of study drugs. Only TEAE will be summarized and analyzed. A separate data listing will be provided only for AE that occurs before treatment.

Each AE will be coded by MedDRA (v23.0) and graded by NCI-CTCAE v4.03. For the same SOC and/or PT, multiple cases of the same events that occur in one subject will be counted only once. For the same AE reported in one subject multiple times but varying in CTCAE grade, the greatest grade episode will be enumerated.

A summary description report will be provided for the number and percentage of subjects experiencing at least one TEAE, treatment-related TEAE (SHR-1210, oxaliplatin, capecitabine, and apatinib), severe TEAE (CTCAE Grade  $\geq 3$ ), TEAE leading to study drug discontinuation/interruption, treatment-related TEAE leading to drug discontinuation/interruption, TEAE leading to dose modification of study drugs, treatment-related TEAE leading to dose modification of the study drugs, TEAE leading to subject withdrawal from treatment, serious adverse event (SAE), and death.

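### The end-of-study definition can cut off the protocol's own 90-day safety follow-up for the last subjects on treatment

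*Protocol*

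**What the plan says.** Protocol section 4.8 gives two possible ends of study: the last subject's last visit, or "the last subject completing 24 months of study treatment after enrollment (whichever occurs first".

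The safety window is tied to each subject's last dose. Section 6.4.1 states "Safety follow-up starts from the last dose of study treatment" and runs it "until 90 days after the last dose", with an on-site visit at day 30 and telephone contacts at days 60 and 90, each with a 7-day window. Section 7.4.2 records AEs over the same period, or until new anti-cancer therapy starts. Section 7.4.3 says SAEs from consent "until 90 calendar days (inclusive) after the last dose will be collected". SAP section 11.4.1 counts an event as treatment-emergent if it occurs or worsens from the first dose "but not later than 90 days after the last dosing of study drugs".

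Section 14 expects the last subject to enrol in December 2018 and then gives "Anticipated study completion: Dec. 2020".

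Section 5.3 caps SHR-1210 at 24 months and adds: "Subjects who do not have progressive disease after 24-month treatment may continue the apatinib monotherapy according to the prescribing information of apatinib". It does not say whether that apatinib is study treatment.

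**The concern.** For a subject treated for the full 24 months, every post-treatment contact falls after month 24. An earlier-of rule with a month-24 trigger therefore selects a date before those contacts. Sites cannot close the study under 4.8 and also complete 6.4.1 inside it for that subject.

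At stake is late AE and SAE ascertainment in subjects with about 21 months or more on treatment. Section 5.2.1 says toxicities of SHR-1210 "may occur shortly after the first dose or several months after the last dose", and AE/SAE incidence and severity is a listed secondary endpoint. The drug-level and anti-drug-antibody samples scheduled at days 30, 60 and 90 after the last dose are exposed in the same way.

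**Working it through.** **Inputs from the documents.** Accrual December 2017 to December 2018, completion December 2020 (section 14). Maximum SHR-1210 duration 24 months (5.3). Safety contacts at days 30, 60 and 90, each ±7 days (6.4.1). N = 98 (section 3), or 48 + 62 = 110 with the non-evaluable allowance (8.2).

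**Inputs assumed.** Even accrual over 12 months, and 5% to 15% of subjects reaching month 24. The documents give neither.

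**1. The plan's completion date.** December 2018 + 24 months = December 2020, exactly the stated date. The schedule allows 0 days after the last-enrolled subject's 24th month.

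**2. Date needed for the 90 days.** For last enrolment on 1 December 2018, month 24 is 1 December 2020 and day 90 is 1 March 2021. For 28 December 2018, day 90 is 28 March 2021, and day 97 (with the +7-day window) is 4 April 2021.

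**3. The triggering subject.** If the last dose falls on the day month 24 is completed, all 90 days are lost. If only the three-weekly infusion set the clock, the last dose could be up to about 21 days earlier, leaving 90 − 21 = 69 days lost. The first visit window opens at day 30 − 7 = 23, so no scheduled safety contact has taken place in either case.

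**4. Who else is exposed.** Only subjects with a last dose fewer than 90 days before study end. Among those who stop exactly at month 24, this means enrolment in the last 90 days of accrual: 90/365 = 24.7% of an even 12-month accrual. Anyone who stopped at least 90 days before study end completes the window.

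**5. How many, if the trigger fires.**
- Enrolled in the last three months: 98/12 × 3 = 24.5.
- Of these, 5% to 15% reaching month 24: 1.2 to 3.7, so about 1 to 4.
- With 110 enrolled: 110/12 × 3 = 27.5, giving 1.4 to 4.1.
- Alternative rate, exponential time on treatment with a median of 6 to 12 months (also an assumption): 0.5^(24/6) = 6% to 0.5^(24/12) = 25%, giving 24.5 × 0.0625 = 1.5 to 24.5 × 0.25 = 6.1.

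These counts cover subjects who stop at month 24. Late enrollees who stop for another reason between about months 21 and 24 would add to them slightly.

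**6. Whether the trigger fires.** This depends on who the last subject is. If it is the last subject enrolled, the trigger rests on one person and, at 5% to 15%, does not fire in 85% to 95% of cases. If it is the last subject still on treatment, the chance is different. Section 4.8 does not say which.

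**The case against.** The strongest reply is that 4.8 is only an administrative definition. The safety duties attach to each subject's last dose. Sponsor termination is listed as ending survival follow-up (6.4.2) but not safety follow-up (6.4.1). Table 14 sets no time limit on collecting treatment-related SAEs, and 7.4.3 still expects suspected-related SAEs after day 90. On this view the duties outlive the end date. Much of that stands, and it is why the point is that follow-up can be lost, not that it will be. It does not remove the conflict. No passage says that visits continue after the defined end of study, the schedule leaves no time for them, and the Table 14 provision does not cover unrelated SAEs, non-serious AEs or the day-30 examinations.

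Four stronger readings are tempting, and the documents do not support them:

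- **That the longest-treated subjects as a group lose their follow-up.** On even accrual, about three quarters of those stopping at month 24 finish their 90 days before December 2020.
- **That any late enrollee reaching month 24 ends the study.** Section 4.8 refers to the last subject.
- **That unobserved time is reported as event-free.** SAP 11.4.1 uses 90 days as an upper bound for classifying an event and reports numbers and percentages of subjects. It gives no event-free estimate. The narrower point stands: a truncated subject stays in the denominator with a shorter window, and nothing in the SAP shows this.
- **That every month-24 completer continuing apatinib has no post-treatment window.** This holds only if that apatinib is study treatment. Section 5.3 can also be read as label use outside the study, in which case it does not arise.

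**Conclusion.** The conflict between 4.8 and sections 6.4.1, 7.4.2 and 7.4.3 is real and visible in the text, and the section 14 dates agree with it. The consequence is conditional. It needs the 24-month trigger to fire, and it then reaches only the triggering subject and others whose last dose falls in the final 90 days. If the last subject stops before month 24, the last visit governs and nothing is lost.

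The likely size is about 1 to 4 of 98 subjects if the trigger fires, given even accrual and an assumed 5% to 15% reaching month 24; the alternative rate in the working gives up to about 6. The section 14 dates are anticipated and given only to the month, so they support the point without proving it. ORR, the sample size and the two-stage decision rules are not affected. The point should be corrected because the repair is cheap, but it does not threaten the primary result.

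**What to change.** - **Section 4.8.** Keep the earlier-of form and move the cap. For example: last subject's last visit, or completion of the 90-day safety follow-up after the last subject's 24 months of study treatment, whichever occurs first. Do not change it to whichever is later: monthly survival follow-up runs to death, loss to follow-up, withdrawal of consent or sponsor termination (6.4.2), so a later-of rule could leave the study open-ended.
- **Last subject.** State whether this means the last enrolled or the last on treatment.
- **Section 14.** Move the completion date to about the end of March or early April 2021.
- **Apatinib after month 24.** Reconcile 5.3 with 4.8 and 6.4.1 on whether it counts as study treatment for the 90-day clock. Until this is settled, the new cap does not by itself secure the window for those subjects.
- **SAP.** Report by cohort how many subjects have a complete 90-day window.

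The cost is one definition, one date, two clarifying sentences and one table line. The extra contacts are already required by 6.4.1. The downside is a database lock about three months later.
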